3.3. Control of Type I Error

For the primary efficacy endpoint in the Part 2 Simon 2-stage cohorts, the 1-sided Type I error will be controlled at 0.05 for each individual cohort expansion. For other endpoints, CIs will be reported at a 95% confidence level. Note that this level of significance does not account for the multiple expansion cohorts.

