3.4.2. Sample Size in Part 2 Safety/Efficacy Expansion Cohorts

3.4.2.1. Part 2 Simon 2-Stage Cohorts

The safety/efficacy expansion in Part 2 will include 2 cohorts per treatment group, subjects with NSCLC who have had disease progression on a prior PD-1 pathway-targeted agent and subjects with MSS CRC. A Simon 2-stage design will be used for each of the cohorts (Simon 1989). The response rates for the historical control (p_0), desired response rates for the combination (p_1), number of subjects needed in Stage 1 (n_1) and Stage 2 (n_2), total number of subjects (n), first

stage threshold declaring cohort undesirable (r_1), and the upper limit of the number of responses in n subjects such that futility of the drug is concluded (r) are provided for each expansion cohort in [Table 10](#). The calculation is based on a 1-sided Type I error of 0.05 and power of 80%.

Table 10: Simon 2-Stage Design

Cohort	Tumor Type	p_0	p_1	n_1	n_2	n	r_1	r
Expansion Cohort A-1	NSCLC subjects who have had disease progression on a prior PD-1 pathway-targeted agent	3%	20%	8	19	27	0	2
Expansion Cohort A-2	MSS CRC	3%	20%	8	19	27	0	2
Expansion Cohort B-7	NSCLC subjects who have had disease progression on a prior PD-1 pathway-targeted agent	3%	20%	8	19	27	0	2
Expansion Cohort B-8	MSS CRC	3%	20%	8	19	27	0	2
Expansion Cohort C-9	NSCLC subjects who have had disease progression on a prior PD-1 pathway-targeted agent	3%	20%	8	19	27	0	2
Expansion Cohort C-10	MSS CRC	3%	20%	8	19	27	0	2

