3.4.2.2. Part 2 Treatment Sequencing Tumor Biopsy Cohorts

Three treatment sequencing tumor biopsy cohorts per treatment group will be enrolled to evaluate epigenetic and tumor microenvironment changes. Five to 8 evaluable subjects per each tumor type will be enrolled in Expansion Cohorts A-3, A-4, B-9 through B-11, and C-11 through C-13. The eligible tumor types are HNSCC, melanoma, UC, and MSS CRC. Subjects with tumor types other than MSS CRC must have had disease progression on a prior PD-1 pathway-targeted agent. Ten subjects with first-line melanoma will be enrolled in Expansion Cohort A-5. See [Table 5](#), [Table 7](#), and [Table 9](#) for more details regarding treatment sequences and biopsy sequences for Treatment Groups A, B, and C, respectively.

Assuming the true rate of subjects positive for the biomarker is 70%, the probability of observing 16 or more subjects out of 25 subjects with the biomarker is 81% for Expansion Cohorts A-3, A-4, B-9 through B-11, and C-11 through C-13, and the probability of observing 6 or more subjects out of 10 subjects with the biomarker is 85% for Expansion Cohort A-5.

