7.2.2. Objective Response Rates and Best Overall Response

A subject is defined as an objective responder if the subject has an overall response of CR or PR at any postbaseline visit prior to first PD. Objective responders will be assessed based on RECIST v1.1.

Objective response rate is defined as the proportion of subjects with objective responses. Objective response rate will be estimated with 95% CIs overall by cohort-specific tumor type. CIs will be calculated based on the method for Simon 2-stage CIs of response rates outlined in Koyama and Chen (2008). Subjects who do not have sufficient baseline data to ascertain response will be included in the denominators in the calculation of ORR.

In general, the best response is determined on subject level using the highest overall response achieved postbaseline prior to and including the first PD, in the order of CR, PR, SD, PD, and NE. Responses of CR, PR, or SD after a response of PD will not be considered in determining best response by RECIST v1.1 criteria. In the case of SD, measurements must meet the SD criteria at least after the date of first dose at a minimum of 56 days (9 weeks – 7-day window). Subjects who fail to meet this criterion will have best overall response of PD if the next available assessment indicated PD, or NE if there is no additional assessment available.

Under RECIST v1.1, the best response is determined by subject using the highest overall response achieved postbaseline prior to and including the first PD, in the order of CR, PR, SD, PD, and NE. Responses of CR, PR, or SD after a response of PD will not be considered in determining best response by RECIST v1.1 criteria. In the case of SD, measurements must meet the SD criteria at least after the date of first dose of study drug at a minimum of 56 days (9 weeks – 7-day window). Subjects who fail to meet this criterion will have best overall

response of PD if the next available assessment indicated PD, or NE if there is no additional assessment available.

For subjects with measurable disease at baseline, the RECIST v1.1 assessment criteria presented in [Table 11](#) can be used to determine the overall disease status at a given time point based on the target lesion, nontarget lesion, and new lesion assessment.

Table 11: RECIST Evaluation Criteria for Overall Response: Measurable Disease at Baseline

Target Lesions	Nontarget Lesions	New Lesions	Overall Response
CR	CR	No	CR
CR	Non-CR/Non-PD	No	PR
CR	NE	No	PR

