9. INTERIM ANALYSES

There are no planned, formal interim analyses for Part 1. Periodic review of accrued clinical data will be conducted by the sponsor and provided to study investigators via teleconferences. Based on review of the most current safety data, the sponsor (in consultation with the study investigators and using the dose-escalation/de-escalation rules) will determine if and at what dose additional subjects should be treated in the study.

Since the study was terminated prior to the interim analyses, no interim analyses will be conducted for Part 2.

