10.1.3. Interim Analyses

- Simon 2-stage design will not be performed due to the early termination of the study. No interim analyses will be conducted for Part 2.

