1.5 Others				
1.5.1	Summary of General Medical History	Safety	X	
2 Efficacy				
2.1.1	Summary of Best Response, Duration of Response Under RECIST v1.1 for Subjects in the Initial Treatment Phase	Response Evaluable		X
2.2.1	Summary of Progression-Free Survival Under RECIST v1.1 for Subjects in the Initial Treatment Phase	Response Evaluable		X
█	█	█		█
2.3.2	Summary of Largest Percentage Reduction in Sum of Diameters of Target Lesions	Response Evaluable		
Safety				

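### The only ORR confidence interval in the SAP is a Simon two-stage interval, although the Simon design was withdrawn and Cohorts A-3 to A-5 and Part 1 have no two-stage parameters

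*SAP*

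**What the plan says.** SAP 7.2.2 sets the reporting unit, "Objective response rate will be estimated with 95% CIs overall by cohort-specific tumor type", and then the method, "CIs will be calculated based on the method for Simon 2-stage CIs of response rates". No other ORR interval method appears in the visible SAP text. The results go into SAP Appendix A, Table 2.1.1, "Summary of Best Response, Duration of Response Under RECIST v1.1 for Subjects in the Initial Treatment Phase", for the response evaluable population.

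The same SAP withdraws the design. SAP 9 reads "Since the study was terminated prior to the interim analyses, no interim analyses will be conducted for Part 2", and SAP 10.1.3 reads "Simon 2-stage design will not be performed due to the early termination of the study".

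Two-stage parameters exist only for the Simon cohorts. SAP 3.4.2.1 says "The safety/efficacy expansion in Part 2 will include 2 cohorts per treatment group". For Group A these are A-1 (NSCLC) and A-2 (MSS CRC), and Table 10 gives both n1 = 8, r1 = 0, n = 27, r = 2. The biopsy cohorts come under SAP 3.4.2.2, "Three treatment sequencing tumor biopsy cohorts per treatment group will be enrolled to evaluate epigenetic and tumor microenvironment changes". They are sized in a single stage on a biomarker rate, with no Stage 1 size or response boundary.

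On the protocol side, 9.4.1 includes other selected solid tumors in the Part 2 primary ORR analysis with a 95% CI. Section 9.4.2 asks for the same in Part 1. The Statistical Methods part of the synopsis names an exact 95% interval for ORR, if the data warrant it.

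**The concern.** A two-stage interval needs the Stage 1 size, the Stage 1 boundary and the stage at which the cohort ended. In A-3 to A-5 and in Part 1 none of these is defined. In A-1 and A-2 the first two exist on paper, but the formal Stage 1 decision was never taken.

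ORR is the Part 2 primary endpoint and a Part 1 secondary endpoint. If the SAP rule cannot be applied to a reported group, whoever programs Table 2.1.1 must choose a method after the data are in hand, and the choice is not prespecified. The numerical question for A-1 and A-2 is separate: does keeping the two-stage formula change the reported limits?

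**Working it through.** **1. The plan's own figures.** With n1 = 8 and r1 = 0 the probability of stopping at Stage 1 is (1 − p)^8. At p0 = 3% this is 0.97^8 = 0.7837, and at p1 = 20% it is 0.80^8 = 0.1678. Both match Protocol 9.6. The full design (continue if X1 ≥ 1, reject if the total is at least 3 of 27) has Type I error 0.0319 and power 0.8002, within the stated 0.05 and 80%. For the biopsy cohorts, P(X ≥ 16 of 25) = 0.811 and P(X ≥ 6 of 10) = 0.850 at a 70% rate, matching the stated 81% and 85%. The design figures are correct.

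**2. Which groups have the inputs.**

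| Reported group | n1 and r1 in the SAP | 95% CI for ORR requested by |
|---|---|---|
| A-1, A-2 | 8 and 0 (Table 10) | Protocol 9.4.1 |
| A-3, A-4, A-5 | none | Protocol 9.4.1 |
| Part 1 | none | Protocol 9.4.2 |

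**3. Can SAP 7.2.2 be read as limited to A-1 and A-2?** It does not say so. SAP 3.3 shows how the document words such a limit when it means one: "For the primary efficacy endpoint in the Part 2 Simon 2-stage cohorts, the 1-sided Type I error will be controlled at 0.05". If the limit is read in anyway, A-3 to A-5 and Part 1 are left with no interval method in the SAP. Both readings leave a gap.

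**4. Size of the effect in A-1 and A-2.** Actual sizes are not stated. Under Protocol 9.6, enrollment is held at the Stage 1 analysis unless enough responders have already been seen. More than 8 subjects should therefore arise only through replacement (Protocol 4.3.2) or after an early response, and in the second case the r1 = 0 condition was met in fact. I assumed one stage-wise construction, with n the final cohort size and k the number of responders:

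- lower limit: solve P(X1 ≥ 1 and total ≥ k) = 0.025
- upper limit: solve 1 − P(X1 ≥ 1 and total ≥ k + 1) = 0.025
- k = 0 stops at Stage 1, so the upper limit is 1 − 0.025^(1/8) = 36.94%

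Exact limits are the usual beta quantiles.

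| Responders/n | Two-stage 95% CI (%) | Exact 95% CI (%) |
|---|---|---|
| 0/8 | 0–36.94 | 0–36.94 |
| 1/8 | 0.32–52.65 | 0.32–52.65 |
| 2/8 | 3.19–65.09 | 3.19–65.09 |
| 1/9 | 0.32–48.25 | 0.28–48.25 |
| 2/9 | 2.81–60.01 | 2.81–60.01 |
| 1/10 | 0.32–44.99 | 0.25–44.50 |
| 2/10 | 2.55–55.61 | 2.52–55.61 |
| 1/12 | 0.32–40.88 | 0.21–38.48 |
| 2/12 | 2.19–48.77 | 2.09–48.41 |
| 3/12 | 5.52–57.21 | 5.49–57.19 |

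With at least one responder the largest difference is 40.88 − 38.48 = 2.40 percentage points. If replaced subjects stay in the denominator and nobody responds, a Stage 1 stop still gives an upper limit of 36.94%. The exact upper limits are 33.63% (0/9), 30.85% (0/10) and 26.46% (0/12).

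**5. What the exact interval would cost if the stopping rule had operated.** I computed its coverage when 0/8 stops the cohort and any response continues it to n. For true ORR up to 35%, coverage is at least 97.5% at n = 8, 9, 10 and 12. Over true ORR from 0.1% to 60% the minima are 96.9%, 95.8%, 96.6% and 95.3% respectively; the last is at n = 12 with a true ORR near 38.5%. Coverage falls slightly below 95% only for larger cohorts near a true ORR of 38% (94.8% at n = 16, 93.7% at n = 27).

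**The case against.** A Simon interval can sensibly be meant only for Simon cohorts, and Table 10 shows which those are. In those cohorts the study ended before the Stage 1 analysis, so 8 or fewer subjects is the natural case, and at 8 the two methods agree exactly. The largest contrast, at 0 responders with 9 to 12 subjects, lies off the design path and rests on one construction; how the cited method treats such sizes cannot be known from these documents. The synopsis already offers an exact interval as a fallback. The analyses are declared descriptive, and no decision hangs on the limits. SAP 10 is partly redacted, and no section 10.1.2 is visible.

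Much of this stands. The effect in A-1 and A-2 is nil or small, and the zero-responder contrast is only illustrative. But the narrow reading moves the gap without closing it, because A-3 to A-5 and Part 1 still have no interval method in the SAP. The synopsis interval is not adopted by the SAP, which names a different one. Hidden text in SAP 10 could record a change, but the visible 7.2.2 sentence would still need correcting.

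One further point is fair. SAP 5.2 combines Parts 1 and 2 by dose level, while 7.2.2 reports by tumor type. In small cohorts the choice of denominator may matter more than the formula. Changing the interval method does not settle that.

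**Conclusion.** The concern holds and should be fixed. The stated ORR interval depends on a design the SAP says will not be performed. It has no defined inputs for A-3 to A-5, and for Part 1 the SAP gives no usable method on either reading. For A-1 and A-2 the consequence is slight: none at n = 8, and at most 2.4 percentage points with one or more responders at the sizes and counts tabulated, up to n = 12. It is visible mainly at 0 or 1 responder.

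These sizes assume n1 = 8, r1 = 0 and the stage-wise construction shown. The paper the SAP cites for its method was not consulted, and actual cohort sizes and response counts are not in the documents. The conclusion about A-3 to A-5 and Part 1 needs none of these assumptions.

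**What to change.** In SAP 7.2.2, replace the two-stage sentence with: *ORR will be presented with a two-sided 95% exact binomial (Clopper-Pearson) CI based on the observed number of subjects in each reported group.* This matches the exact interval in the protocol synopsis, needs no stage information and works for A-1 to A-5 and for Part 1. Record the change in SAP 10 unless the redacted text already lists it. When making the edit, also state which groups are reported, so that 7.2.2 agrees with SAP 5.2.

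The cost of changing the interval is one SAP sentence, one line in SAP 10 if needed and one line of code. No new data are required.

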9. STATISTICS

9.1. Study Populations

The safety population includes all subjects enrolled in the study who received at least 1 dose of study drug (azacitidine, INCB057643, INCB059872, pembrolizumab, or epacadostat). All safety analyses will be based on the safety population.

The full analysis set includes all subjects enrolled in the study who received at least 1 dose of study drug (azacitidine, INCB057643, INCB059872, pembrolizumab, or epacadostat) and had at least 1 postbaseline assessment or discontinued treatment. All efficacy analyses will be based on the full analysis set.

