2.3.1. Primary Endpoints

- Part 1: Safety and tolerability will be assessed by monitoring the frequency, duration, and severity of AEs; through physical examinations; by evaluating changes in vital signs and ECGs; and through clinical laboratory blood and urine sample evaluations.
- Part 2: Objective response rate, defined as the percentage of subjects having a CR or PR, will be determined by investigator assessment of radiographic disease as per RECIST v1.1.

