5.3. Analysis Populations

5.3.1. Response Evaluable Population

The response evaluable population includes all subjects enrolled in the study who received at least 1 dose of study drug (epacadostat, pembrolizumab, or azacitidine), completed a baseline scan, and met at least 1 of the following criteria:

- The subject has ≥ 1 postbaseline scan.
- The subject has been on study for a minimum of 70 days of follow-up.
- The subject has discontinued from treatment.

All RECIST-based response analyses will be conducted using the response evaluable population.

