7.2.5. Progression-Free Survival

Progression-free survival will be assessed by RECIST v1.1.

[figure not shown]
Censoring for PFS will follow the algorithm outlined in [Table 12](#), which is based on the FDA Guidance for Industry: Clinical Trial Endpoints for the Approval of Cancer Drugs and Biologics ([FDA 2007](#)).

The KM estimate of median PFS will be presented with its 95% CI. The 95% CI will be calculated using Brookmeyer and Crowley's method (1982).

Table 12: Evaluation and Censoring of Progression-Free Survival

Situation	Outcome	Date of Progression or Censoring
No baseline tumor assessments	Censored	Date of Day 1
No valid postbaseline response assessments	Censored	Date of Day 1
Progression documented between scheduled response assessments	Progressed	Date of first overall response of PD
No progression	Censored	Date of last valid radiologic assessment (not NE and not missing)
Study discontinuation for undocumented progression	Censored	Date of last valid radiologic assessment (not NE and not missing)
Study discontinuation for toxicity or other reason	Censored	Date of last valid radiologic assessment (not NE and not missing)
New anticancer treatment started	Censored	Date of last valid radiologic assessment (not NE and not missing) on/before starting a new anticancer treatment.
Death before first progressive response assessment	Progressed	Date of death
Death between adequate response assessments	Progressed	Date of death
Death or progression after more than 1 missed assessment	Censored	Date of last valid radiologic assessment (not NE and not missing) prior to death

Under RECIST v1.1, PFS is defined as the length of time between the baseline visit (Day 1) and the earlier of death or first assessment of PD. Date of death will be determined using the Death Report, Survival Follow-Up, and Subject Status eCRFs.

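### For a treated subject with no completed baseline scan, SAP 5.3.1 and 7.2.2 give opposite rules for the ORR denominator, and the SAP's efficacy set departs from the protocol's with no visible record of the change

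*SAP*

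**What the plan says.** ORR is the primary endpoint for Part 2 (SAP 2.3.1: "Part 2: Objective response rate, defined as the percentage of subjects having a CR or PR").

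The SAP has two provisions on who is counted:

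- SAP 5.3.1 defines the response evaluable population as treated subjects who "completed a baseline scan, and met at least 1 of the following criteria". The criteria are a postbaseline scan, treatment discontinuation, or "The subject has been on study for a minimum of 70 days of follow-up". It adds: "All RECIST-based response analyses will be conducted using the response evaluable population". Appendix A assigns this population to Table 2.1.1 (best response and DOR) and Table 2.2.1 (PFS).
- SAP 7.2.2 says of the ORR: "Subjects who do not have sufficient baseline data to ascertain response will be included in the denominators in the calculation of ORR".

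For PFS, the first row of SAP Table 12 covers "No baseline tumor assessments" and censors those subjects at Day 1.

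Protocol 9.1 defines a different efficacy set. The full analysis set is subjects who took one or more doses and "had at least 1 postbaseline assessment or discontinued treatment. All efficacy analyses will be based on the full analysis set". It has no baseline-scan condition. The SAP defines no full analysis set.

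**The concern.** A programmer who meets a treated subject with no baseline scan is told by 5.3.1 to leave the subject out of the ORR and by 7.2.2 to keep the subject in. Table 12 points the same way as 7.2.2: it supplies a censoring rule for subjects whom the PFS population cannot contain.

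The choice has a direction. Under SAP 7.2.1, response is judged from changes in lesions, so a subject with no baseline scan cannot be shown to be a responder. Leaving such a subject out shrinks the denominator and never the numerator. In an open-label study with investigator-assessed response, the denominator of the primary endpoint should be settled before the data are seen. ORR will still be reported after early termination, so the question remains live.

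Separately, the protocol says "All efficacy analyses will be based on the full analysis set". A SAP that uses another set should say that it has done so.

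**Working it through.** **1. The plan's own figures.** The documents give no count of treated subjects without a baseline scan, so there is no stated denominator effect to reproduce. The cohort sizes used below come from the Simon design in SAP Table 10: n1 = 8, r1 = 0, n = 27, r = 2, p0 = 3%, p1 = 20%.

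- Early termination = (1 − p)^8. This gives 0.97^8 = 0.7837 and 0.80^8 = 0.1678, as stated in Protocol 9.6.
- Probability of declaring activity = sum over x = 1 to 8 of P(X1 = x) · P(X2 ≥ 3 − x), with X1 ~ Bin(8, p) and X2 ~ Bin(19, p). This gives 0.0319 at 3% and 0.8002 at 20%, consistent with the stated 0.05 limit and 80% power.

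The design reproduces. From here on, 27 and 8 serve only as illustrative denominators.

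**2. The rules side by side, for treated subjects.**

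| Subject | SAP 5.3.1 | SAP 7.2.2 | Protocol 9.1 |
|---|---|---|---|
| Baseline scan completed but inadequate; discontinued | in | in | in |
| No completed baseline scan; discontinued | **out** | **in** | in |
| Baseline scan completed; still on treatment at 70 days or more with no postbaseline assessment | in | no separate rule | out |
| Baseline scan completed; still on treatment before 70 days; postbaseline assessment other than a scan | out | no separate rule | in, if a non-imaging assessment counts |

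The SAP contradicts itself only in the second row. Rows two to four show the three departures from the protocol set: the added baseline-scan condition, the 70-day route, and *scan* in place of *assessment*.

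**3. Size for ORR.** With x responders among n subjects, of whom k have no baseline scan, 7.2.2 gives x/n and 5.3.1 gives x/(n − k). The value of k is an assumption; 0 to 3 of 27 is shown.

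| x | k = 0 | k = 1 | k = 2 | k = 3 |
|---|---|---|---|---|
| 3 | 3/27 = 11.1% | 3/26 = 11.5% | 3/25 = 12.0% | 3/24 = 12.5% |
| 5 | 5/27 = 18.5% | 5/26 = 19.2% | 5/25 = 20.0% | 5/24 = 20.8% |

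In a cohort of 8 with one responder: 1/8 = 12.5%, 1/7 = 14.3% (k = 1), 1/6 = 16.7% (k = 2). With k = 0 the rules agree. With x = 0 the ORR is 0% under either.

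**4. Size for PFS.** A subject censored at Day 1 leaves the risk set before any later event, so the Kaplan-Meier estimate is the same whether the subject is censored there or excluded. Only the number of subjects and the censored count change.

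**5. The change list.** The visible entries are:

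- SAP 10.1.1: RECIST v1.1 only; no confirmation of response.
- SAP 10.1.3: no Simon design or Part 2 interim analysis.
- SAP 10.2: no figures; no analyses of Groups B and C.

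None mentions the population. However, a redaction follows the first bullet of 10.1.1, and no 10.1.2 is visible.

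**The case against.** The strongest reply is that the two SAP rules address different conditions. Insufficient baseline data is not the same as no baseline scan, and 7.2.2 can be read as operating inside the 5.3.1 population, on subjects whose scan was done but was inadequate. That stands in part: a reader might infer that the rules conflict for everyone with poor baseline data, and they do not. But nothing in 7.2.2 confines it to subjects with a completed scan, and a subject with no scan falls within its plain words. Table 12 row 1 shows that the SAP elsewhere provides for such subjects. That row may be carried over from the FDA guidance on which the table is based, and an unused row does no harm by itself.

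Second, the group may be empty. Protocol 7.6.1.1 requires imaging within 28 days before the first dose, measurable disease is an inclusion criterion, and Protocol 3 does not allow eligibility deviations. This stands as to size. Protocol 4.3.2 does foresee accidental enrolment of ineligible subjects, so the case cannot be ruled out.

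Third, a reader might infer from 1/8 or 3/27 that a go/no-go decision is at risk. The documents do not support that. SAP 10.1.3 drops the Simon design, SAP 5.2 pools Parts 1 and 2 by dose level, and 7.2.2 reports ORR by cohort-specific tumor type.

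Fourth, a reader might infer that the change of set was concealed. With part of 10.1 blacked out, only its absence from the visible text can be stated. The SAP was also written against Protocol Amendment 3, whereas the protocol at hand is Amendment 4. The Amendment 4 log names no change to Section 9.1, so the full analysis set was presumably already there.

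**Conclusion.** The point holds in a limited form. For a treated subject with no completed baseline scan, SAP 5.3.1 with Appendix A excludes the subject from ORR and PFS, while 7.2.2 counts the subject in the ORR and Table 12 gives a PFS rule. The response evaluable set also departs from the Protocol 9.1 full analysis set in three ways, with no visible record.

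The likely numerical effect is nil or small: about 0.4 to 0.8 percentage points per excluded subject in a cohort of 27 with 3 to 5 responders, and 1.8 points for one subject in a cohort of 8 with one responder. These figures rest on assumed counts and on cohort sizes that may not have been reached. The upward direction belongs to the baseline-scan condition. The 70-day route works the other way, since it can only add subjects who have no postbaseline assessment and so no response.

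It is also tempting to describe the protocol set as all treated subjects. It is not: it further requires a postbaseline assessment or treatment discontinuation. All treated subjects is the safety population.

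The correction is worth making because the endpoint is primary and the change costs almost nothing.

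**What to change.** 1. Replace the SAP 5.3.1 definition with the Protocol 9.1 full analysis set: one or more doses, plus either a postbaseline assessment or treatment discontinuation. Merely deleting the baseline-scan condition would leave the 70-day route and the *scan* wording in place.
2. Use that set for ORR and PFS, and relabel Appendix A Tables 2.1.1 and 2.2.1. Table 12 row 1 then has subjects to apply to. The target-lesion analysis in SAP 7.2.4 remains limited to subjects with target lesions at baseline.
3. State in 7.2.2 that subjects in the set without a baseline or postbaseline scan count as non-responders. The present text implies this for baseline only.
4. Record in SAP 10.1.1 any difference from Protocol 9.1 that the sponsor chooses to keep, such as requiring a scan rather than an assessment.

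The cost is a few lines of SAP wording and one population flag. The downside is that ORR may be slightly lower if any such subject exists.
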